8.4.2 UNANTICIPATED PROBLEM REPORTING

All UADEs will be reported to the sponsor within 72 hours from when the research team became aware of the event.

9 STATISTICAL CONSIDERATIONS

9.1 STATISTICAL HYPOTHESES

The primary endpoint in the ARREST clinical trial is survival to hospital discharge.

The primary study hypotheses are

$$H_0: p_E = p_C \text{ versus } H_A: p_E \neq p_C$$

where p_E denotes the probability of response in the target population under Early ECMO Facilitated Resuscitation and p_C the probability of response under Standard ACLS Resuscitation with response defined by surviving to hospital discharge. The study will reject the null hypothesis H_0 when there is a suitably large posterior probability that either $p_E > p_C$, i.e. ECMO is superior, or $p_E < p_C$, i.e. ECMO is inferior. The threshold has been chosen to ensure type I error rate control at the nominal 0.05 level using computer simulation. The posterior probabilities will be based on a Bayesian Beta-Binomial model described below. The study sample size has been selected to provide 90% power for rejecting the null hypothesis under the targeted alternative scenario with $p_E = 0.37$ versus $p_C = 0.12$.

The primary null hypothesis that will be tested in this trial is there is no difference in the probability of a favorable outcome between the group randomized in the field to **Early ECMO Facilitated Resuscitation** and the group randomized to **Standard ACLS Resuscitation**.

The primary alternative hypothesis is that success rates in the **Early ECMO Facilitated Resuscitation** group will be 37%, while those in the **Standard ACLS Resuscitation** group will be 12%.

The primary endpoint is dichotomous. The most appropriate analysis given the Bayesian design (see below) is based on a beta-binomial model for the posterior distributions.

Bayesian Adaptive Design and Monitoring

This trial has a Bayesian adaptive design. What this means is that there will be periodic evaluation of the primary outcomes in the two groups. At such evaluations, if there is a difference in success rates between the two groups, the ratio of patients randomized will be weighted toward the better of the two groups.

Probability Model

Let Y_i indicate whether the i^{th} participant survives to hospital discharge which we assume follows a Bernoulli distribution with probability of response p_a when this participant is assigned to group $a = E$ or C . We specify independent Uniform(0,1) \equiv Beta(1,1) prior distributions for p_E and p_C . Let N_a denote the number of participants assigned to group a and X_a the number of responses. It follows that the posterior distribution for p_a is Beta(X_a+1 , $N_a - X_a + 1$) and

$$\text{Prob}(p_E > p_C | \text{Data}) = \int_0^1 [1 - F(y | X_E + 1, N_E - X_E + 1)] f(y | X_C + 1, N_C - X_C + 1) dy$$

where $F(y | a, b)$ and $f(y | a, b)$ respectively denote the Beta(a,b) cumulative distribution and probability density functions. Note that $\text{Prob}(p_E < p_C | \text{Data}) = 1 - \text{Prob}(p_E > p_C | \text{Data})$. We calculate $\text{Prob}(p_E > p_C | \text{Data})$ in R v3.5.1 using adaptive quadrature via the `integrate()` function.

Group Sequential Adaptive Design

We will calculate $\text{Prob}(p_E > p_C | \text{Data})$ each time we ascertain an evaluable outcome on 30 participants, and stop the trial for superiority when $\text{Prob}(p_E > p_C | \text{Data}) \geq 0.986$, or for inferiority when $\text{Prob}(p_E < p_C | \text{Data}) \geq 0.986$. If the trial does not stop, the next group of enrollees will be randomized to ECMO with probability equal to the current value of $\text{Prob}(p_E > p_C | \text{Data})$ subject to the restriction that the randomization ratio may not exceed 3:1 in either direction. The initial cohort of patients will be randomized 1:1. Upon ascertaining evaluable outcomes on 150 participants, if neither posterior probability threshold for superiority or inferiority is exceeded the trial will be stopped with a failure to reject the null. This maximum sample size was chosen to provide 90% power for the targeted alternative scenario of with $p_E = 0.37$ versus $p_C = 0.12$ as evidenced by the computer simulation study reported below.

Operating Characteristics

We carried out a computer simulation study to assess the operating characteristics of the proposed adaptive design. To this end, we simulated 10,000 trials following the proposed adaptive design by generating outcome data under a null scenario with $p_E = p_C = 0.12$ and the targeted alternative scenario with $p_E = 0.37$ versus $p_C = 0.12$. When aiming to obtain up to $n = 150$ evaluable outcomes, Table 1 indicates the proposed adaptive design controls the type I error rate at the nominal 0.05 level and provides 90% power for the targeted alternative benefit. While the adaptive design is unlikely to stop early under the null scenario with an average sample size of 148.5, it is likely to stop early under the targeted alternative scenario with an average sample size of 81.6. Breaking these figures out by the average number assigned to each group shows that under the null, on average, the adaptive design with randomize about 74 people to each group, whereas under the targeted alternative, on average, only 29 participants are randomized to the inferior standard group and 52.5 to ECMO group.

Table 1: Simulated operating characteristics of the adaptive trial design based on 10,000 trials with $n = 150$ under the two key scenarios. Posterior probability threshold is 0.986 throughout the trial. Null scenario assumes 0.12 response probability in both groups, alternative assumes 0.37 versus 0.12.				
Scenario	Proportion of Trials Rejecting Null Hypothesis	Average Trial Sample Size	Average Number Assigned to ECMO Group	Average Number Assigned to Standard Group
Null	0.048	148.5	74.2	74.3
Alternative	0.905	81.6	52.5	29.2

To account for up to 15% withdrawal, we will aim to enroll up to 175 participants and thereby ensure up to 150 participants with evaluable outcomes for the primary hypothesis test assessment.

Stopping Criteria

We will allow early stopping for superiority or inferiority of ECMO, i.e. symmetric bounds. That is, we plan to stop the study when either posterior $\text{Prob}(p_E > p_C \mid \text{Data}) \geq 0.986$ or posterior $\text{Prob}(p_E < p_C \mid \text{Data}) \geq 0.986$. In the former situation, we will declare ECMO superior, and in the latter, we will declare ECMO inferior. These assessments will be carried out at pre-planned sample sizes throughout the study, not continuously. In particular, we will assess these posterior probabilities each time we complete follow-up on 30 participants. If the trial does not stop for either superiority or inferiority, the randomization ratio will be modified for the next group of 30 participants as described previously.

Secondary outcomes will include the occurrence of ECMO-related complications, survival to hospital discharge with mRS ≤ 3 , survival to 3 and 6 months, survival to 3 and 6 months with mRS ≤ 3 , functional status at discharge, 3 and 6 months (mRS score; Cerebral Performance Category [CPC] score), cost per patient (based on billing charges), and cost per life saved (based on billing charges).

9.2 SAMPLE SIZE DETERMINATION

The primary outcome is binary, with success defined as survival to hospital discharge. The appropriate analysis, given the Bayesian design, is computed using the posterior beta-binomial distribution. We hypothesize a treatment effect of 12% success in the **Standard ACLS Resuscitation** group and 37% success in the **Early ECMO Facilitated Resuscitation** group. Assuming success rates of 12% vs. 37% in the 2 groups and 90% power and a type 1 error rate of 0.05, the required sample size is $N = 148$ evaluated patients. We inflated this figure to account for 15% rate of withdrawal prior to hospital discharge and for false positive activation and randomizations (which may occur due to the emergent nature of the randomization) to obtain a target sample size for randomization of $N = 174$.

9.3 POPULATIONS FOR ANALYSES

The primary population for analysis is the set of patients who are randomized immediately following hospital arrival and are not excluded afterward by conditions that cannot be determined emergently. The patients that are found to meet prespecified exclusion criteria for the ARREST trial post randomization will be excluded. These are the only patients excluded from the ITT population.

It may happen in rare cases that a patient randomized to **early ECMO facilitated resuscitation** does not receive ECMO, or conversely that a patient randomized to **standard ACLS resuscitation** does receive ECMO because they became clinically unstable after they entered the CCL with ROSC. These cases, if they are found to meet eligibility and exclusion criteria, will be analyzed according to the ITT principle: 1) those randomized to receive **early ECMO facilitated resuscitation** will be classified in the early ECMO

facilitated resuscitation group irrespective of whether or not they received ECMO, and 2) those randomized to receive **standard ACLS resuscitation** will be classified in the standard ACLS resuscitation group irrespective of whether or not they received ECMO.

The secondary 'as-treated' population will be comprised of two groups of patients: (1) those who receive ECMO, regardless of treatment assignment, and (2) those who do not receive ECMO (again regardless of treatment assignment).

As specified elsewhere in this Protocol, there are pre-specified subpopulations of interest. These are defined by: 1) gender, 2) age group (< 55 years old versus \geq 55 years old), 3) presence versus absence of coronary artery disease (> 70% stenosis), and 4) 911 call to CCL arrival (< 50 minutes vs. \geq 50 minutes). These will be treated as strata in Mantel-Haenszel analyses and in multivariable logistic analyses of the data. Such analyses will include terms for interaction of the randomized treatment group assignment with the stratifying factors.

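### At the target effect, the planned logistic models with treatment-by-subgroup interactions usually have at least one term with no finite maximum-likelihood estimate, and the plan has no sparse-data rule

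*Combined protocol and SAP*

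**What the plan says.** Section 9.3 lists sex, age at 55, coronary disease (more than 70% stenosis) and time from 911 call to CCL arrival at 50 minutes. Of these it says "These will be treated as strata in Mantel-Haenszel analyses and in multivariable logistic analyses of the data", and then: "Such analyses will include terms for interaction of the randomized treatment group assignment with the stratifying factors". It gives no penalised or exact method, no minimum number of survivors and no fallback if a model cannot be estimated.

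Sections 4.2 and 9.4.7 warn that subgroup power will be low, and 9.4.7 calls the comparisons exploratory. Neither mentions that an estimate may not exist.

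Section 9.1 gives the amount of data to expect. At the target effect, on average "only 29 participants are randomized to the inferior standard group and 52.5 to ECMO group", and its Table 1 note says: "Null scenario assumes 0.12 response probability in both groups, alternative assumes 0.37 versus 0.12".

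**The concern.** A joint model with an intercept, arm, four factors and four arm-by-factor interactions has 1 + 1 + 4 + 4 = 10 parameters. Because every factor interacts with arm, fitting it amounts to fitting a separate five-parameter model in each arm. In the standard arm those five parameters rest on three or four survivors.

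If one level of a factor has no survivors in an arm, the maximum-likelihood interaction odds ratio is zero or infinite. Software seldom stops at this point. It usually prints a huge coefficient, a larger standard error and a Wald p-value close to 1. Low power means a valid but imprecise estimate; here there is no estimate, and the output can be misread as evidence of a uniform effect. The risk is highest when the trial stops early for benefit, and section 9.4.1 says the results will inform a decision on a multicentre trial.

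**Working it through.** **Inputs from the documents**
- Survival 0.37 versus 0.12, or 0.12 in both arms under the null (9.1, Table 1).
- Beta(1,1) priors; "Posterior probability threshold is 0.986 throughout the trial"; "we will assess these posterior probabilities each time we complete follow-up on 30 participants", up to 150.
- "The initial cohort of patients will be randomized 1:1"; afterwards the ECMO probability equals the current posterior probability, limited to 0.25–0.75 (9.1).
- Coronary disease in 52/62 = 84% of the local cohort, so 16% without it (2.1).
- Mean age 53 in that cohort (2.3.2), taken as roughly a 50/50 split at 55.

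**Assumptions.** The documents give no split for sex or for time at 50 minutes, so a range is shown. Factors are taken as independent of outcome and known for everyone.

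**Step 1: reproduce Table 1.** 10,000 simulated trials were run under each of three ways of implementing the allocation.

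| Scenario | Quantity | Plan | Reproduced |
|---|---|---|---|
| Target | Rejection rate | 0.905 | 0.901–0.905 |
| Target | Average N | 81.6 | 81.7–82.5 |
| Target | ECMO / standard | 52.5 / 29.2 | 52.5–53.1 / 29.2–29.4 |
| Null | Rejection rate | 0.048 | 0.044–0.051 |
| Null | Average N | 148.5 | 147.0–147.3 |

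**Step 2: standard-arm survivors at the target effect.** 0.12 × 29.2 = 3.5. The simulation gives mean 3.5 and median 3, with none in about 12% of trials and at most two in about 46%.

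**Step 3: one factor with its interaction.** This model is saturated, so it has no finite fit if any arm-by-level group has no survivors or only survivors. For a fixed 29 standard-arm patients and a level of share q, the chance that some level has no survivors is

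(1 − 0.12q)^29 + (1 − 0.12(1 − q))^29 − 0.88^29.

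- q = 0.50: 0.166 + 0.166 − 0.025 = 0.31.
- q = 0.16: 0.570 + 0.046 − 0.025 = 0.59.

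Early stopping makes the standard arm often much smaller than 29, which raises these figures. In the simulated design:

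| Smaller level | 50% | 40% | 30% | 20% | 16% | 10% |
|---|---|---|---|---|---|---|
| Interaction inestimable | 42–44% | 46% | 51% | 59–61% | 66–67% | 78% |

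**Step 4: joint model with four interactions.** Except in the 25/50/80/30 row, which counts trials with an empty cell for at least one factor, existence of the fit was tested by a linear-programming separation check within each arm.

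| Level shares (%) | Target | Null |
|---|---|---|
| 50/50/50/50 | 62–64% | 33% |
| 30/50/30/50 | 70% | 46% |
| 25/50/80/30 | 77–78% | 64% |
| 20/50/16/30 | 83–84% | 73% |

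A simple empty-cell count for the balanced case gives 61%. Almost all target-effect failures arise in the standard arm. All four one-factor interactions fail together in about a third of trials (31–37% across runs and splits).

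**Step 5: by stopping look, target effect**

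| N at stop | Share of trials | Standard-arm survivors (mean) | Joint failure, 50/50 | Joint failure, 20/50/16/30 |
|---|---|---|---|---|
| 30 | 24% | 0.8 | 100% | 100% |
| 60 | 27% | 2.0 | 85% | 97% |
| 90 | 19% | 3.6 | 60% | 86% |
| 120 | 13% | 5.3 | 30% | 71% |
| 150 | 18% | 8.1 | 8% | 49% |

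If 5–20 further patients accrue after an early stop, joint failure is 53–60% (balanced) or 80–82% (20/50/16/30).

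**Step 6: what is printed.** Take survivors/patients of 3/15 and 0/14 in the standard arm and 10/26 and 9/26 in the ECMO arm. Ordinary logistic regression returns an interaction odds ratio of about 1.3 billion, standard error about 12,900 and Wald p = 0.9987. In a saturated model, Firth's penalty amounts to adding one half to each survivor and death count:

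[(9.5/17.5)/(0.5/14.5)] ÷ [(10.5/16.5)/(3.5/12.5)] = 15.7/2.27 = 6.9.

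That is finite and can carry an honest, wide interval.

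**The case against.** **The text does not fix one joint model.** Section 9.3 speaks of analyses in the plural. One factor at a time, a balanced factor fails in a minority of trials (about 43%), and failure in most trials needs a smaller level of about 30% or less. This stands, so both readings are reported.

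**A reader might infer that the subgroup analysis yields nothing usable more often than not.** The figures do not show that. The 60–84% is the chance that at least one term fails. Fitted separately, at least one of the four interactions is estimable in about two thirds of trials.

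**Other planned methods tolerate sparse cells.** The Mantel-Haenszel pooled odds ratio stays finite unless the standard arm has essentially no survivors (about 12%). It estimates a stratified effect, though, not an interaction. Logistic models without interactions fail in only 16–23%.

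**A reader might extend the point to the secondary endpoints in 9.4.3.** Fisher's exact test is already offered there, and nothing was calculated for those endpoints. That extension is not supported.

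**The stakes are limited.** The analyses are labelled exploratory and the primary beta-binomial decision does not use them. This limits the importance, but neither label tells a reader that a printed odds ratio may be an artefact.

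**Conclusion.** The concern holds in this form. At 37% versus 12%, the joint interaction model has at least one term without a finite maximum-likelihood estimate in about 60% of trials with balanced factors and about 77–84% with clearly unequal splits. Fitted singly, the interaction fails in about 43% for a balanced factor and about 66% for coronary disease at 84/16. Under the 12% null the joint figure is about 33–73%.

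The coronary split comes from the protocol's earlier cohort, the age split is inferred from a mean, and the sex and time splits are assumptions. Coronary status and CCL arrival time may also be missing for standard-arm patients who die in the ED without reaching the CCL. Dropping patients from a model cannot restore a finite fit, so on this count the rates are, if anything, too low. Cannot be estimated here means by ordinary maximum likelihood; penalised or exact methods would work but are not planned.

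**What to change.** In 9.3 and 9.4.7, replace the joint maximum-likelihood interaction model with Firth-penalised logistic models, one factor at a time, reporting the interaction with a profile-likelihood interval rather than a Wald p-value. Show survivors/patients by arm and level beside every estimate. Where an arm has no patients at a level, give counts only, since no method can then estimate the interaction. For example, with 15 standard-arm patients and a 16% no-disease level this has probability 0.84^15 = 0.07. State how patients with unknown coronary status or CCL arrival time are handled. Beta-binomial posteriors by level, with 95% credible intervals, may be added.

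The change needs plan wording and a few lines of code, with no extra data. It has two costs. Mutual adjustment between factors is lost, and estimates shrink toward no effect in very small cells, more so with Beta(1,1) priors. At 16% without coronary disease, the standard arm expects 29.2 × 0.16 = 4.7 patients and 0.56 survivors, so the posterior mean is 1.56/6.7 = 0.23. ECMO expects 52.5 × 0.16 = 8.4 patients and 3.1 survivors, giving 4.1/10.4 = 0.39. A true difference of 0.25 would appear as about 0.16. In a 50/50 subgroup it would appear as about 0.21 (10.7/28.25 − 2.75/16.6). The rule should be fixed before outcome data by arm are seen, so that the fallback is not chosen after the fact.

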Legend: Probability of survival to hospital discharge (A), and favorable neurologic outcome at hospital discharge (B), among those with refractory cardiac arrest at increasing increments since commencement of professional resuscitation (with 95% confidence intervals).⁶⁵

- **The temporal effect of ECMO on potential survival.**⁶⁶

We recently compared the probability of survival with CPC of 1 or 2 based on time of CPR before ECPR initiation at the University of Minnesota and the survival with CPC of 1 or 2 from the ALPS trial⁴⁸ database for patients with the ARREST inclusion criteria. This paper is under review in JACC. As the data show, ECMO initiation appears to offer a higher chance of survival compared to standard ACLS.

Below we show the main figure of our manuscript submitted to the Journal of American College of Cardiology that describes the effect of the duration of CPR with and without the availability of ECPR (VA ECMO based resuscitation).

Relationship of CPR Duration and Survival

Time (min)	0-9	10-19	20-29	30-39	40-49	50-59	60-69	70-79	80-89	90-99	Total
MRC-ECPR	0	0	7	9	19	29	31	25	16	7	143
ALPS	70	151	102	95	99	69	29	11	3	7	636

Legend: Survival with Cerebral Performance Category of 1 or 2 with the Minnesota Resuscitation Consortium protocol (University of Minnesota and ARREST trial early ECMO arm) compared to the ALPS trial patient population with similar inclusion criteria of age. Of the 218 patients that received CPR longer than 40 minutes in the ALPS trial no one survived. On the contrary the survival probability in the University of Minnesota ECPR protocol showed 100% neurologically intact survival for patients receiving professional CPR for 20-29 minutes prior to initiation of ECMO. However, even with ECPR, survival declines over time with an increase in mortality of 24% with every 10 minutes of delay beyond 29 minutes. Despite this time dependence, in the setting of ECPR, survival remains possible even with very long CPR durations as the University of Minnesota cohort demonstrates a stable survival rate of approximately 20% with CPR extending between 60 and 89 minutes. The table below the figure shows the number of patients at risk in 10-minute increments of CPR duration of the two cohorts. As of note, the **average duration of CPR** in the ALPS cohort was 34±5 minutes and for our University of Minnesota cohort 61±7 minutes almost double. Data from **Bartos JA et al JACC 2019; under review**

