9.4.7 SUB-GROUP ANALYSES

The primary study endpoint will be compared between: 1) males versus females, 2) study subjects < 55 versus ≥55 years old, 3) presence versus absence of coronary artery disease (>70% stenosis), and 4) 911 call to ECMO initiation <50 versus ≥50 minutes. It should be noted, however, that *a priori*, the power to detect significant treatment effects in these subgroups, which are substantially smaller than the trial's entire cohort, will be low. These are exploratory. The sample sizes of these defined subgroups are such that the power to test hypotheses in these subgroups is substantially smaller than that for the main hypothesis.

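### Effect modification by age is tested only after splitting at 55, which wastes information if the effect changes gradually with age; a continuous age-by-arm term would be the better planned test

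*Combined protocol and SAP*

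**What the plan says.** Section 9.4.7, like 4.2, lists four subgroup factors for the primary endpoint. Age enters as "study subjects < 55 versus ≥55 years old". Section 9.3 repeats the age split and says of all four factors: "These will be treated as strata in Mantel-Haenszel analyses and in multivariable logistic analyses of the data". It adds that these analyses will contain interactions between randomised arm and each factor. No section plans a linear or spline term for age.

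Section 9.4.5 lists age, and several intervals from the 911 call in minutes, among the baseline descriptives.

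The time factor is also split, at 50 minutes, but it is defined in two ways: 911 call to CCL arrival in 9.3, and 911 call to ECMO initiation in 4.2 and 9.4.7.

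Sections 4.2 and 9.4.7 both say that power in the subgroups will be low, and 9.4.7 labels these analyses exploratory. No power is stated for any interaction test.

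**The concern.** A two-level age factor treats a 20-year-old and a 54-year-old as alike, and a 54-year-old and a 55-year-old as different. The documents give no reason to expect the effect of early ECMO to change abruptly at 55. If it changes gradually, the split discards information the trial already holds, in analyses whose power the plan already concedes is low.

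What is at stake is modest: how well the trial can show whether the benefit varies with age. Section 9.4.1 says the results will inform the decision on a multicentre trial of generalisability, so a better-powered description is worth having if it costs nothing.

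**Working it through.** **1. The plan's own figures.** The inputs are in 9.1 and 9.2: "Assuming success rates of 12% vs. 37% in the 2 groups and 90% power and a type 1 error rate of 0.05", Beta(1,1) priors, a look every 30 patients up to 150, threshold 0.986 at each look, and allocation following the posterior probability with a 3:1 cap. Simulating this design (20,000 trials per scenario) gives:
- power 0.902 (stated 0.905)
- type I error 0.0487 (stated 0.048)
- average size under the alternative 82.5, of whom 53.1 ECMO and 29.4 standard (stated 81.6, 52.5 and 29.2)

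The design reproduces. Two sizes are therefore relevant below: 75/75 at the maximum, and 52/29 at the expected stopping size under the target effect.

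**2. Information kept by a split.** For a normal covariate split so that a proportion p lies on one side, the share of information kept is φ(z_p)² / [p(1−p)]. At the median this is 2/π = 0.64. The documents give a mean age of 53 for the centre's earlier cohort (2.3.2) but no SD. Assuming mean 54 and SD 12, limited to 18-75, about 44.5% are 55 or over. The correlation between age and the indicator is then 0.805, so the split keeps 0.805² = 0.65.

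In power terms for a two-sided 0.05 test at a median split: if the continuous test has power 0.40, its noncentrality is 1.96 − 0.253 = 1.707. The split multiplies this by √0.637 = 0.798, giving 1.362, and power Φ(1.362 − 1.96) = 0.275. Similarly, 0.80 falls to 0.61.

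The correlation is symmetric. If the truth is a step at the cut, it is the linear term that keeps only about 0.65.

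**3. Simulated interaction test.** Age is distributed as in step 2, and survival at age 54 is set to 37% (ECMO) and 12% (standard). The test is a likelihood-ratio test at 0.05 of the treatment-by-age term in a logistic model with age as the only covariate. Slopes are log-odds per decade (ECMO, standard) and are assumed, since the documents give none. With 1,500 trials per scenario the Monte Carlo standard error is at most √(0.25/1500) = 0.013. Repeat runs of the same scenario differed by up to about 0.05.

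| Slopes per decade | 75/75: continuous vs split | 52/29: continuous vs split |
|---|---|---|
| (−1.0, 0) | 0.65 vs 0.43 | 0.38 vs 0.25 |
| (−0.6, +0.3) | 0.57 vs 0.44 | 0.36 vs 0.27 |
| (0, −1.0) | 0.76 vs 0.54 | 0.43 vs 0.31 |
| (−0.5, 0) | 0.23 vs 0.17 | 0.145 vs 0.13 |
| (−0.3, 0) or (−0.5, −0.2) | about 0.14 vs 0.10 | about 0.10 vs 0.09 |

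Relative losses at 75/75 for the steep rows are (0.65−0.43)/0.65 = 34%, (0.57−0.44)/0.57 = 23% and (0.76−0.54)/0.76 = 29%. For the milder rows they are (0.23−0.17)/0.23 = 26% and (0.14−0.10)/0.14 = 29%, but the absolute losses are only 6 and 4 points. With no true interaction, both codings reject in about 6-8% of trials, so the gain is not bought with false positives.

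**4. The opposite truth.** With a step of 2.0 log-odds at 55 and 75/75 patients, the split has power 0.57 and the continuous term 0.41 (0.45 in a repeat run). With a step of 1.5 the figures are 0.39 and 0.28.

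**The case against.** **The slopes are steep.** A slope of −1.0 per decade implies ECMO survival of about 87% at age 30 (logit 0.37 = −0.53; −0.53 + 2.4 = 1.87) and 7% at age 74 (−0.53 − 2.0 = −2.53). The pattern (0, −1.0) raises overall standard-arm survival to about 17.6%, away from the planned 12%. This stands. It is why the milder rows belong beside the steep ones, and why the absolute gain may be only a few points.

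**A linear test is favoured by linear truths.** This also stands: the ranking reverses for a step at 55. But nothing in the documents points to a step there.

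**A reader might infer that a third of the power is lost as a general figure or an upper limit.** The documents do not support that. The loss is relative and depends on a shape and an age spread that they do not give. Other linear age scenarios at 150 patients gave 27% to 47%, and a step gives a gain.

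**A reader might extend the point to time**, because 2.3.2 says that "survival declines over time with an increase in mortality of 24% with every 10 minutes of delay beyond 29 minutes". That sentence describes prognosis by CPR duration within one ECPR-treated cohort, not a difference between arms. The same legend reports survival holding at about 20% from 60 to 89 minutes, which is a plateau rather than a straight line. Moreover, a standard-arm patient who dies in the ED has neither a CCL arrival time nor an ECMO start time, so minutes times arm cannot be fitted to the whole trial under either definition.

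**A reader might infer that eligibility for a later trial would rest on these tests.** Section 9.4.1 speaks only of deciding whether to run one.

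**The planned model is multivariable, with several interactions.** The simulation has one covariate, so its figures illustrate the effect of coding and do not give the power of the planned model.

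**Conclusion.** The point holds for age, as a minor improvement. Under modification roughly linear on the log-odds scale, splitting at 55 keeps about 0.65 of the information. In the scenarios tabulated, relative power at 75/75 falls by roughly a quarter to a third. In absolute terms that is 13 to 22 points for steep slopes and about 4 to 6 for milder ones. At about 82 patients neither coding reached 0.5 in any tabulated scenario.

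The conclusion rests on an assumed age distribution, assumed slopes and a single-covariate test, and it reverses for a true step at 55. For time, no size can be attached until the interval is defined. The low power is already acknowledged, the analyses are exploratory, and the primary beta-binomial comparison in 9.4.2 is untouched.

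**What to change.** In 9.3 and 9.4.7, state that effect modification by age will be tested in the logistic model by the product of arm and age in years, entered linearly. Keep the two-category tables and the Mantel-Haenszel strata, which need categories, for display and as a check on linearity. Bring 4.2 into line.

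For time, first reconcile 9.3 with 4.2 and 9.4.7 to one interval that exists in both arms; 911 call to hospital arrival is a candidate, since it precedes randomisation. Only then use minutes times arm in the same way.

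The cost is a few lines of wording, with no new data and no change in sample size. The downside to state openly is lower power if the true pattern is a step at the cut-point.
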